1 INTRODUCTION

The purpose of this statistical analysis plan (SAP) is to provide all information that is necessary to perform the statistical analyses of study MG0017. It also defines the summary tables, figures and listings (TFLs) to be included in the Clinical Study Report (CSR) according to the protocol.

This SAP includes safety, efficacy, pharmacokinetics (PK) and pharmacodynamics (PD) analyses. Changes to protocol-planned analysis are documented in Section 6.3. Table, Figure and Listing specifications are contained in a separate document.

This SAP is based upon and assumes familiarity with protocol amendment 3.0 dated 30 November 2022.

If a future protocol amendment necessitates a substantial change to the statistical analysis of study data, this SAP may be amended accordingly. The content of this SAP is compatible with the International Council for Harmonization (ICH)/Food and Drug Administration (FDA) E9 Guidance documents.

The statistical analyses and production of the outputs described in the SAP will be conducted using SAS software version 9.4 or above. The final analyses and outputs will be approved by UCB.

1.1 Objectives and Estimands/Endpoints

The estimand corresponding to the primary objective and primary safety analyses are described below. The estimands corresponding to the secondary objectives and secondary analyses are also described below.

Table 1.1: Objectives and estimands/endpoints

Objectives	Estimands/endpoints
Primary	
To evaluate the safety and tolerability of switching from intravenous (IV) Complement component 5 (C5) inhibitors to subcutaneous (SC) Zilucoplan (ZLP) in study participants with generalized Myasthenia Gravis (gMG)	
The primary safety endpoints are:
 
• Incidence of Treatment Emergent Adverse Events (TEAEs) over the Main Treatment Period• Incidence of TEAEs leading to withdrawal of study medication over the Main Treatment Period
Secondary	
To evaluate the efficacy of SC ZLP after switching from IV C5 inhibitors in study participants with gMG	The secondary efficacy estimand is:

Objectives	Estimands/endpoints
	
 Treatment: ZLP administered by daily SC injections (0.3mg/kg/day) Target population: Adult study participants with gMG currently receiving an IV C5 inhibitor approved for the treatment of gMG according to the protocol-specified inclusion/exclusion criteria Endpoint: Change from Baseline (CFB) to Week 12 in Myasthenia Gravis -Activities of Daily Living (MG-ADL) score Intercurrent event handling: The intercurrent events considered in this study are: 
 ICE1: Administration of rescue therapy or changes in Standard of Care (SoC) dose regimens. Data collected at and after the point of the intercurrent event will be used as collected to gain understanding of clinical practice. ICE2: Participant discontinuation from the study. It will be assumed that the participant had remained on their treatment (regardless of rescue therapy administration) throughout the study (i.e., a "hypothetical strategy" assuming participants did not discontinue the study and remained on treatment). Population level summary: The mean of the endpoint
To evaluate the efficacy of SC ZLP after switching from IV C5 inhibitors on an additional efficacy endpoint in study participants with gMG	
The secondary efficacy endpoint is:
 
 CFB to Week 12 in the Quantitative Myasthenia Gravis (QMG) score 
This endpoint will be analyzed following the same estimand structure as defined for the MG-ADL score. The endpoint assessed will change accordingly.

To evaluate safety and tolerability of SC ZLP after switching from IV C5 inhibitors on additional safety measures in study participants with gMG	
The secondary safety endpoints are:
 
 Incidence of serious TEAEs over the Main Treatment Period Incidence of study withdrawal over the Main Treatment Period
Other	
To further explore the efficacy of SC ZLP on additional efficacy endpoints after switching from IV C5 inhibitors in study participants with gMG	
The other efficacy endpoints are:
 
 Time to first receipt of rescue therapy over the Main Treatment Period Change in SoC therapy medication dose regimen for gMG during the Main Treatment Period

Objectives	Estimands/endpoints
	
 • Achievement of Minimal Manifestation Status per Myasthenia Gravis Foundation of America Post Intervention Status (MGFA-PIS) at Week 12 without rescue therapy • Achieving minimal symptom expression (MSE), defined as an MG-ADL of 0 or 1 at Week 12 without rescue therapy • CFB to Week 12 in QMG subscores: ocular, bulbar, respiratory, limb • CFB to Week 12 in Myasthenia Gravis MG Quality of Life 15 Item scale revised (MG-QOL15r) score • MG-ADL score responder rate (responder is defined as achieving \geq 3-point improvement from Baseline [decrease] at Week 12 and not having taken rescue therapy) • QMG score responder rate (responder is defined as achieving \geq 5-point improvement from Baseline [decrease] at Week 12 and not having taken rescue therapy)
To explore the time needed for administration of SC ZLP	
The other endpoint is:
 
 • Time needed for administration of SC ZLP
To explore study participants' treatment satisfaction following the use of SC ZLP	
The other endpoint is:
 
 • CFB to Week 12 in 9 item Treatment Satisfaction Questionnaire for Medication (TSQM-9) scores
To explore study participant preference following the use of SC ZLP	
The other endpoint is:
 
 • Patient Preference assessment at Week 12
To further evaluate the safety and tolerability of SC ZLP after switching from IV C5 inhibitors on other safety measures in study participants with gMG	
The other safety endpoints are:
 
 • CFB to Week 12 in clinical laboratory tests • CFB to Week 12 in physical examination • ECG • Columbia-Suicide Severity Rating Scale (C-SSRS) • Incidence of TEAEs
To evaluate the PK of SC ZLP after switching from IV C5 inhibitors	
The other PK endpoint is:
 
 • Plasma concentrations of ZLP and its major metabolites over the Main Treatment Period (██████████)
To evaluate the PD of SC ZLP after switching from IV C5 inhibitors	
The other PD endpoint is:
 
 • sheep red blood cell (sRBC) lysis assay for evaluation of classical complement pathway activation over the Main Treatment Period

C5=complement component 5; CFB=change from Baseline; C-SSRS=Columbia-Suicide Severity Rating Scale; gMG=generalized myasthenia gravis; IV=intravenous; MG-ADL=Myasthenia Gravis-Activities of Daily Living; MG-QOL15r=Myasthenia Gravis – Quality of Life revised; MGFA-PIS=Myasthenia Gravis

Objectives	Estimands/endpoints
Foundation of America Post-Intervention Status; MSE=Minimal Symptom Expression; PD=pharmacodynamic(s); PK=pharmacokinetic(s); QMG= Quantitative Myasthenia Gravis; SC=subcutaneous; SoC=standard of care; sRBC=sheep red blood cell; TEAE=treatment-emergent adverse event; TSQM-9=9-item Treatment Satisfaction Questionnaire for Medication; ZLP=zilucoplan	

1.2 Study design

MG0017 is a Phase 3b, multicenter, open-label, single-arm study to evaluate the safety, tolerability, and efficacy of ZLP in study participants with gMG switching from their current IV C5 inhibitor to SC ZLP.

To be eligible to participate in this study, participants must be adults (≥ 18 years of age) with a documented diagnosis of gMG (Myasthenia Gravis Foundation of America (MGFA) Class II-IVa), currently receiving an IV C5 inhibitor approved for the treatment of gMG for at least 3 months (for eculizumab) or 4 months (for ravulizumab) prior to Screening (with the last dose being administered at the Screening Visit ± 3 days), considered to have a clinically stable disease as per the Investigator's judgment prior to Screening, and willing to switch from their current IV C5 inhibitor to SC ZLP.

The planned enrollment is 20 study participants in the US.

The study includes a 2-week or 8-week Screening Period (for participants receiving eculizumab or ravulizumab, respectively), a 12-week Main Treatment Period, and an optional Extension Treatment Period. A Safety Follow Up (SFU) Visit should be performed 40 days (± 7 days) after the last dose of study medication.

The Screening Visit should be scheduled to coincide with the regularly scheduled study participant's IV C5 inhibitor administration (± 3 days). Up to and including the time of the Screening Visit, study participants will continue to receive their IV C5 inhibitor at the recommended dose regimen. The last regularly scheduled IV C5 inhibitor administration cannot occur beyond Day -14 (± 3 days) of the Screening Period for study participants receiving eculizumab or beyond Day -56 (± 3 days) of the Screening Period for study participants receiving ravulizumab to ensure approximately a 2-week or 8-week interval between the last regularly scheduled IV C5 inhibitor administration and the first SC ZLP administration during the Main Treatment Period, respectively.

At the end of the Screening Period and in case of no more than a 2-point change in study participants' MG-ADL score compared to the Screening Visit, study participants will enter the Main Treatment Period and will switch to SC ZLP (IV C5 inhibitor should not be administered after the Screening Visit). On Day 1, study participants will receive ZLP 0.3mg/kilogram (kg) administered SC. Following in-clinic education and training, all study participants will self-inject daily SC doses of study medication for the subsequent 12-weeks. Single-use pre-filled syringes in injection devices will be provided for use during the study. Of note, there will be no washout period during the study where study participants are not receiving treatment for MG.

During the Main Treatment Period, study participants will be contacted via phone call at Week 1, Week 4, and Week 8 to assess safety and tolerability. During these phone call visits, the MG-ADL assessment will also be performed. Study participants will return to the clinic at Week 2 and Week 12 to evaluate safety, tolerability, and efficacy. Additional assessments will

include questionnaires, PK, and PD. Safety assessments will include adverse event (AE) monitoring, physical examination, clinical laboratory tests, and C-SSRS.

The time needed for preparation and administration of SC ZLP will also be measured during the Main Treatment Period in accordance with the Schedule of Activities.

Study participants are expected to remain on a stable dose regimen of all medications unless medically indicated changes become necessary. All SoC therapy medications for gMG should be kept at the same dose regimen throughout the study, including corticosteroids and immunosuppressant therapy (IST) drugs. If rescue therapy becomes necessary due to major deterioration of a study participant's clinical status, or risk of MG crisis as per the Investigator's judgment, the study participant may receive intravenous immunoglobulin G (IVIG) or plasma exchange (PLEX) treatment as rescue therapy.

Additionally, if deemed needed as per the Investigator's judgment, study participant may be readministered their previous IV C5 inhibitor after discontinuation of the study medication.

All study participants who complete the Main Treatment Period will have the option to continue ZLP treatment in the Extension Treatment Period after the Week 12 visit. If a study participant withdraws from the study during the Main Treatment Period, the participant will complete an Early Withdrawal (EW) Visit followed by a SFU Visit 40 days (± 7 days) after the last dose of study medications. Participants who opt not to continue into the Extension Treatment Period will complete a SFU Visit 40 days (± 7 days) after the last dose of study medication.

The Extension Treatment Period consists of in-clinic visits every 12 weeks (± 7 days) and will continue until all participants are withdrawn, until ZLP is approved and available in the US, or until further notice from the Sponsor. During these visits, ZLP accountability and resupply will be performed, medications updated, and safety will be assessed. Participants who withdraw or discontinue ZLP during the Extension Treatment Period will complete a Withdrawal Visit followed by a SFU Visit 40 days (± 7 days) after the last dose of study medication. Participants who transition to commercially available ZLP will complete a Withdrawal Visit but will not require a SFU Visit. If by the time a participant completes the Main Treatment Period ZLP is commercially available, the participant may transition to commercially available ZLP directly following the Week 12 visit at the end of the Main Treatment Period.

2 STATISTICAL HYPOTHESES

The null hypothesis for the secondary efficacy endpoint of the secondary efficacy estimand is that the ZLP CFB in Week 12 MG-ADL is greater than the non-inferiority (NI) margin of 2. The alternative hypothesis is that the ZLP CFB in Week 12 MG-ADL is lower than the NI of 2.

This secondary efficacy endpoint will be tested at the 1-sided alpha of 0.025.

No multiplicity adjustment is planned in this study.

3 SAMPLE SIZE DETERMINATION

The secondary efficacy estimand will investigate if the Week 12 MG-ADL score is noninferior to the Baseline MG-ADL score with an NI margin of 2. It is assumed that the Week 12 CFB has

a standard deviation (SD) of 3 and that the true CFB is 0. Given a sample size of 20 study participants, the study has approximately 80% power to detect this, based on a 1-sided alpha of 0.025.

4 POPULATIONS FOR ANALYSIS

- Enrolled Set (ES): The ES will include all study participants who signed the ICF.
- Intention-to-Treat (ITT) Population: The ITT Population will include all eligible study participants. Efficacy analyses will be performed on the ITT in case there is a difference of at least 5 participants as compared to the modified Intention-to-Treat (mITT) Population.
- Modified ITT Population (mITT): The mITT Population will include all eligible study participants who received at least 1 post-Baseline dose of study medication and had at least 1 post-Baseline assessment. The mITT Population will be used for all efficacy analyses.
- Safety Set (SS): The SS will include all study participants who received at least 1 dose of study medication and will be used for the safety analyses.
- Pharmacokinetic Per-Protocol Set (PK-PPS): The PK-PPS will include all study participants in the safety population who received at least 1 dose of study medication and had at least 1 quantifiable PK measurement post dose of study medication without important protocol deviations that would affect the PK. The PK-PPS will be used for all PK analyses.
- Pharmacodynamic Per-Protocol Set (PD-PPS): The PD-PPS will include all study participants in the safety population who received at least 1 dose of study medication and had at least 1 quantifiable PD measurement post dose of study medication without important protocol deviations that would affect the PD. The PD-PPS will be used for all PD analyses.

5 STATISTICAL ANALYSES

5.1 General Considerations

Statistical analysis and generation of tables, figures, participant data listings, and statistical output will be performed using SAS® Version 9.4 or higher. All tables and listings will use Courier New font size 9.

All clinical study data will be presented in participant data listings.

Descriptive statistics will be displayed to provide an overview of the study results. For continuous variables, descriptive statistics will include number of participants with available measurements (n), mean, SD, median, minimum, and maximum. For categorical variables, the number and percentage of participants in each category will be presented. Unless otherwise noted, the denominator for percentages will be based on the number of participants included in the respective analysis set.

Participants with missing data can generally be accounted for using the following approaches:

- For summaries of demographics and Baseline characteristics: summarize percentages based on all participants in the analysis set and include a “Missing” category (corresponding to

participants with missing data for the variable being summarized) as the last row in the list of categories being summarized.

- For summaries of efficacy and safety variables, unless otherwise specified: summarize percentages based only on those participants with observed data for the variable being summarized. As the denominator may be different from the number of participants in the analysis set being considered, the denominator should be displayed in the table. The general format for displaying this will be “n/Nsub (%).”

Unless otherwise noted, all percentages will be displayed to one decimal place. No percentage will be displayed for zero counts, and no decimal will be presented when the percentage is 100%.

For the purpose of the tabulations the lower and upper confidence limits for the percentages will be truncated at 0 and 100% respectively.

For PK concentrations, summary statistics will include geometric mean, geometric coefficient of variation (CV), 95% confidence intervals (CIs) for geometric mean, arithmetic mean, SD, median, minimum, and maximum. All summaries of PK variables will be based on the observed values. No imputation will be used.

Decimal places for descriptive statistics will always apply the following rules:

- “n” will be an integer;
- Mean, SD, and median will use one additional decimal place compared to the original data;
- CV [%] will be presented with one decimal place;
- Minimum and maximum will have the same number of decimal places as the original value.

Derived variables in general will display the mean, SD and median to 1 more decimal place than the variables used in the derivation. If the number of decimal places reported in the raw data is varied, then use either the maximum raw number of reported decimal places or 3, whichever is the lowest, as a guide for the descriptive statistics.

Statistical test of secondary efficacy variable will be presented as p-values rounded to four decimal places. P-value less than 0.001 will be presented as “<0.001” and p-value greater than 0.999 will be presented as “>0.999.” Statistical comparison will be one-sided and will be performed at the 0.025 level of significance.

If no participants have data at a given time point, for example, then only n=0 will be presented. However, if n<3, present the n, minimum and maximum only. If n=3, n, mean, median, minimum and maximum will be presented only. The other descriptive statistics will be left blank

Demographics and baseline characteristics will be analyzed in the mITT population. Prior and Concomitant medications will be done in the SS. Efficacy analyses will be done in the mITT population. Safety, PK and PD analyses will be done respectively in the SS, PK-PPS and PD-PPS.

Once the last study participant has completed the SFU, or the last study participant has prematurely discontinued prior to reaching the SFU, the database will be locked. TFLs will be produced.

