## 7.2 Participant discontinuation/withdrawal from the study

Study participants are free to withdraw from the study at any time, without prejudice to their continued care.

A study participant may withdraw from the study at any time at his/her own request or may be withdrawn at any time at the discretion of the Investigator for safety, behavioral, compliance, or administrative reasons.

If the study participant withdraws consent for disclosure of future information, the Sponsor may retain and continue to use any data collected before such a withdrawal of consent.

If a study participant withdraws from the study, he/she may request destruction of any samples taken and not tested, and the Investigator must document this in the site study records.

See the Schedule of Activities (Section 1.3) for data to be collected at the time of study discontinuation.

Participants should be withdrawn from the study if any of the following events occur:

1. Participant develops an illness that would interfere with his/her continued participation.
2. Participant is noncompliant with the study procedures or medications in the opinion of the Investigator.
3. Participant restarts administration of previous IV C5 inhibitor or is administered a different IV C5 inhibitor (Section 6.5.2).
4. Participant withdraws his/her consent.
5. The Sponsor or a regulatory agency requests withdrawal of the participant.
6. Participant has active suicidal ideation with some intent to act without specific plan, as indicated by a positive response (“Yes”) to question 4 of the “Since Last Visit” version of the C-SSRS. The participant should be referred immediately to a mental healthcare professional and may be withdrawn from the study based upon the Investigator’s judgment of benefit/risk of continuing the participant in the study/on study medication.

7. Participant has active suicidal ideation with a specific plan as indicated by a positive response (“Yes”) to question 5 of the “Since Last Visit” version of the C-SSRS. The participant should be referred immediately to a Mental Healthcare Professional and must be withdrawn from the study.

Investigators should contact the Medical Monitor, whenever possible, to discuss the withdrawal of a study participant in advance.

If a study participant withdraws from the study, the participant will not be replaced.

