## **9.6 Handling of dropouts or missing data**

For secondary efficacy analyses, missing data will be handled according to the secondary efficacy estimand definition:

- For missing data of participants who discontinue from the study, a missing at random assumption will be used for imputation. This is in relation to the assumption that the participant had remained on their treatment throughout the study.
- For other missing data, the same missing at random assumption as the one used for imputing missing data of participants who discontinue from the study will be applied.

Missing or partial dates for safety evaluations will be imputed and full details of these algorithms will be presented in the SAP. Baseline is defined as the last nonmissing pretreatment measurement (Section 9.2). Therefore, data from the Screening Visit (if available) will be used as Baseline values if data are missing at Day 1.

No further imputations of any other missing data are planned.

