5.3.2 Other efficacy endpoint analyses

The other efficacy endpoints are:

- Time to first receipt of rescue therapy over the Main Treatment Period
- Change in SoC therapy medication dose regimen for gMG during the Main Treatment Period
- Achievement of Minimal Manifestation Status per MGFA PIS at Week 12 without rescue therapy
- Achieving MSE, defined as an MG ADL of 0 or 1 at Week 12 without rescue therapy
- CFB to Week 12 in QMG subscores: ocular, bulbar, respiratory, limb
- CFB to Week 12 in MG-QOL15r score
- MG-ADL score responder rate (responder is defined as achieving ≥ 3 -point improvement from Baseline [decrease] at Week 12 and not having taken rescue therapy)
- QMG score responder rate (responder is defined as achieving ≥ 5 -point improvement from Baseline [decrease] at Week 12 and not having taken rescue therapy)

The MG-ADL score responder rate will be assessed based only on participants having an MG-ADL score ≥ 3 at Baseline, while the QMG score responder rate will be assessed based only on participants having an QMG score ≥ 5 at Baseline.

All those endpoints will be analyzed using descriptive statistics, as mentioned in the Section [5.1](#).

The time to first receipt of rescue therapy over the Main Treatment Period and over the Overall Treatment Period will be analyzed as time-to-event, using Kaplan-Meier plots.

For the MG-ADL and QMG responder rate the number and percentage of participants who have a reduction (i.e., improvement) of $\geq X$ will be summarized in the mITT at Week 12. The improvement values will start at the maximum level of worsening and will continue to the maximum level of improvement seen in the study. Note this is an extension of the “Achieving a ≥ 3 -point reduction in MG-ADL Score at Week 12 without rescue therapy” and “Achieving a ≥ 5 -point reduction in QMG Score at Week 12 without rescue therapy” endpoints.

Individual line plots with individual values of Total MG-ADL, QMG and MG-QoL15r scores will be created in mITT.

For participants infected with COVID-19 as per the AE page, CFB in QMG and MG-QOL15r score will be listed by visit separately.

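### SAP 5.3.2 sets no non-response rule for a missing Week 12 value, so some early leavers drop out of the responder, MSE and Minimal Manifestation rates and others can count as Week 12 successes

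*SAP*

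**What the plan says.** SAP 5.1 opens with a default that, unless otherwise noted, "the denominator for percentages will be based on the number of participants included in the respective analysis set". A more specific rule for efficacy and safety variables follows: "summarize percentages based only on those participants with observed data for the variable being summarized". Because the resulting denominator may be smaller than the analysis set, "the denominator should be displayed in the table".

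SAP 5.3.2 covers the four binary Week 12 endpoints: MG-ADL response, QMG response, MSE and Minimal Manifestation. It refers them back to that section: "All those endpoints will be analyzed using descriptive statistics". Each definition makes rescue a failure, for example "Achieving MSE, defined as an MG ADL of 0 or 1 at Week 12 without rescue therapy" and "Achievement of Minimal Manifestation Status per MGFA PIS at Week 12 without rescue therapy". Section 5.3.2 also limits the MG-ADL responder rate to participants with a baseline score of at least 3, and the QMG rate to those with at least 5. It does not say what happens when the Week 12 value is missing.

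The missing-at-random handling in Protocol 9.6 and SAP 5.1.1.7.1 applies to the secondary efficacy analyses. Beyond the date and Baseline rules given there, Protocol 9.6 states: "No further imputations of any other missing data are planned".

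Protocol 7.2 lists as a reason for withdrawal: "Participant restarts administration of previous IV C5 inhibitor or is administered a different IV C5 inhibitor". Protocol 6.5.2 asks for an EW Visit before that return. SAP 5.1.1.1.4 maps EW assessments to the next visit at which the assessment in question is scheduled.

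**The concern.** In a switch study, leaving early, and above all going back to the previous class of infusion, is itself information about how the switch went. A rate computed only among participants with a Week 12 value is conditional on having stayed. If those who left were mostly failures, the rate describes a selected group and reads better than the experience of everyone who switched.

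The rule also sits awkwardly with the endpoints. All four already treat rescue as failure, yet a participant who withdraws to resume an IV C5 inhibitor may simply not be counted. For the main MG-ADL endpoint, SAP 5.3.1.1.2 plans a sensitivity analysis that assigns the worst score after rescue, a standard-of-care change or study discontinuation. The binary endpoints have no counterpart.

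Because mapping depends on each instrument's own schedule, the same early leaver can be outside one denominator and inside another.

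**Working it through.** **Plan's own figure.** The documents give no expected value for these four rates. The one related figure is the power of the MG-ADL noninferiority test, about 80% with 20 participants (Protocol 9.8, SAP 3). With margin 2, SD 3, true change 0 and 1-sided alpha 0.025, the noncentrality is 2/(3/√20) = 2.981 on 19 degrees of freedom. The exact one-sample t power is 80.7%, which agrees. A denominator rule for percentages does not touch that test.

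**Step 1: which early leavers have a value at Week 12.** Inputs are the Schedule of Activities (Protocol 1.3) and the mapping rule (SAP 5.1.1.1.4).

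| Endpoint | Scheduled post-baseline visits | EW value reaches Week 12 if the participant leaves | Dropped if the participant leaves |
|---|---|---|---|
| MG-ADL response, MSE | Weeks 1, 2, 4, 8, 12 | after Week 8 | by Week 8 |
| QMG response | Weeks 2, 12 | after Week 2 | by Week 2 |
| Minimal Manifestation | Week 12 | at any time | only if there is no EW assessment |

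Anyone who leaves with no EW assessment, for example lost to follow-up, is missing for all four. The item-level carry-forward in SAP 6.1.5 repairs a single missing item, not a missing visit.

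**Step 2: rescued participants.** Protocol 6.5.4 has participants who are kept on zilucoplan after rescue complete their assessments to the end of the study. They have a Week 12 value, are failures by definition and stay in the denominator. For a participant who is rescued and then withdrawn with no value mapped to Week 12, the outcome is already fixed as non-response, but the SAP does not say whether that person is counted.

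**Step 3: size.** Let N be the denominator population, x the achievers and k those with no value at Week 12 after mapping.

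- Observed-case rate: x/(N-k)
- Withdrawal or missing counted as failure: x/N
- Ratio of the two: N/(N-k)
- Best case, all missing succeed: (x+k)/N

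The documents give neither k nor x. The table assumes N = 20, x of 4 or 10, and k from 0 to 5.

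| k | N/(N-k) | x = 10: observed vs 50.0% | x = 4: observed vs 20.0% |
|---|---|---|---|
| 0 | 1.000 | 50.0% | 20.0% |
| 1 | 1.053 | 52.6% | 21.1% |
| 2 | 1.111 | 55.6% | 22.2% |
| 3 | 1.176 | 58.8% | 23.5% |
| 4 | 1.250 | 62.5% | 25.0% |
| 5 | 1.333 | 66.7% | 26.7% |

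The baseline-score restriction can make N smaller for the responder rates, and the same k then weighs more. With an assumed 12 eligible, 2 missing and 5 responders, the rates are 5/10 = 50% and 5/12 = 42%.

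**Step 4: one worked mix (assumed).** Take 20 participants with 10 achievers at Week 12, 2 rescued who stay, and 2 who leave between Weeks 2 and 8 with an EW Visit. For MSE the planned rate is 10/18 = 55.6%; counting the leavers as failures gives 10/20 = 50.0%. For Minimal Manifestation both EW values map to Week 12, so the denominator stays 20. If one of those EW values shows Minimal Manifestation without rescue, the rate becomes 11/20 = 55.0%, although that participant left before Week 12.

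**The case against.** The strongest reply is that little is hidden and little depends on it. These are descriptive endpoints in a 20-participant single-arm study, with no test or comparator. The reduced denominator is printed beside each rate. Withdrawal is a secondary endpoint in its own right, rescue and withdrawal have Kaplan-Meier plots, intercurrent events are listed, and missing MG-ADL values are tabulated by visit. All of that stands and limits the weight of the point. But a displayed denominator shows how many are absent, not that they may be failed switches.

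A second reply is that the default sentence in SAP 5.1 points to the full analysis set, and 5.3.2 summarises response in the mITT. The efficacy bullet is more specific and would ordinarily govern; that two readings are possible is itself a reason to settle it.

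A reader might also infer more than the documents support:

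- **That rescued participants leave the denominator.** Those who reach Week 12 stay in as failures. In the mix above, removing them would give 10/16 = 62.5%, which is not what the plan produces.
- **That participants rescued and then withdrawn are removed.** The SAP is silent. Responder status could fairly be called observed once rescue has occurred.
- **That everyone who withdraws or switches back disappears from all four rates.** An EW Visit is expected before a return to an IV C5 inhibitor, and its values reach Week 12 for Minimal Manifestation, for QMG after Week 2 and for MG-ADL after Week 8.
- **That the bias always favours zilucoplan.** The observed-case rate is never below the rate that counts missing as failure, but it lies between that and the best case. Withdrawal can be administrative, and the unseen outcomes are unknown.

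**Conclusion.** The gap is real but narrow. The observed-data rule applies, and no non-response rule covers a missing Week 12 value. MG-ADL response and MSE are the most exposed (leaving by Week 8), then QMG response (leaving by Week 2). Minimal Manifestation is exposed only when there is no EW assessment, but it is the clearest case where mapping can turn an early value into a Week 12 success.

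Relative to counting withdrawal as failure, the rate is higher by 0% at k = 0, 5% at k = 1, 11% at k = 2 and 25% at k = 4 when N = 20, and by more where the baseline restriction shrinks N. These sizes rest on assumed k. They also take counting withdrawal as failure as the reference, a choice that suits endpoints which already count rescue that way. The noninferiority conclusion is not affected. The change is worth making because it is cheap and removes an ambiguity.

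**What to change.** In SAP 5.3.2, override the general percentage rule for MG-ADL response, QMG response, MSE and Minimal Manifestation:

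- Count as non-response any rescue use, any withdrawal before Week 12 regardless of a mapped EW value, and any missing Week 12 value.
- Use as denominator all mITT participants or, for the two responder rates, all who meet the stated baseline-score restriction.
- Keep the observed-case rate, with its displayed denominator, as supportive.

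This also settles the rescued-then-withdrawn case and whether a mapped EW value may count as a Week 12 success. The cost is a short addition to the SAP and a changed denominator in the affected tables. The reported rates become slightly less favourable, and participants who leave for administrative reasons are counted as failures; the supportive rate shows how much that matters.
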